5.2. Participant Dispositions

The number of HHCs in the following disposition categories will be summarized throughout the study by intervention group and overall:

- Participants screened
- Participants randomized
- Participants who received study drug
- Participants who discontinued study drug
- Reasons for discontinuation of study drug
- Participants who completed the study
- Participants who terminated study prematurely
- Reasons for termination of study

This summary will be created separately for the safety, the primary, the secondary and the complete study population.

Listings of participants will be provided for the following categories:

- Participants who discontinued study drug
- Participants who terminated study prematurely
- Participants who were unblinded during the study period
- Participants who were randomized yet did not receive study drug.

5.3. Primary Endpoint(s) Analysis

5.3.1. Definition of Endpoint(s)

All samples will be tested by a DENV RT-qPCR with a qualitative output. A sample is considered positive for DENV RNA in case the result is 'target detected'.

In addition, all samples will be tested by the EUROIMMUN enzyme-linked immunosorbent assay (ELISA). The results of this test will be reported in relative units (RU)/ml and will be interpreted as follows:

- <8 RU/ml: negative

- ≥ 8 to <11 RU/ml: borderline

^{**} Up to 60 minutes after first study intervention intake

^{*} PK substudy/other participants

– ≥11 RU/ml: positive

A sample is considered DENV NS1 positive if the qualitative DENV NS1 result is positive (ie. quantitative DENV NS1 result ≥11 RU/ml). Samples are considered DENV NS1 negative for missing ELISA results and for borderline or negative qualitative ELISA results (ie. quantitative DENV NS1 result <11 RU/ml).

The primary endpoint is defined as presence or absence of a laboratory-confirmed DENV infection between baseline and the last day of dosing + 1 day. Presence of a laboratory-confirmed DENV infection is defined as a positive DENV RNA or DENV NS1 protein (ELISA) test result. Missing results between baseline and last day of dosing + 1 day will not be considered.

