All secondary endpoints will be analyzed graphically and descriptively as described in the Statistical Analysis Plan (SAP). For continuous variables, descriptive statistics (n, mean, standard deviation [SD], median, minimum, maximum, and 95% CIs) will be calculated. For categorical variables, frequency tables and corresponding 95% CIs will be presented.

Safety Analyses

Adverse Events

For each AE, the percentage of participants who experience at least 1 occurrence of the given event will be summarized by intervention group. Solicited AEs will be summarized by intervention group. All AEs will be analyzed descriptively.

Summaries, listings, datasets, or participant narratives may be provided, as appropriate, for those participants who die, who discontinue intervention due to an AE, who experience a severe or a serious AE, or who experience rashes requiring rash-management procedures (Section 10.2).

Clinical Laboratory Tests

Laboratory data will be summarized by type of laboratory test. Frequency tabulations of the laboratory abnormalities will be made either by grading according to the modified Division of Acquired

Immunodeficiency Syndrome (DAIDS) Table for Grading the Severity of Adult and Pediatric Adverse Events, supplemented with WHO toxicity grading scales t, or with classes for below, within, and above normal ranges for parameters that are not graded for either DAIDS and WHO grading scales. A listing of participants with any laboratory results outside the reference ranges will be provided. A listing of participants with any markedly abnormal laboratory results (Grade 3 or Grade 4) will also be provided.

Electrocardiograms

The effects on cardiovascular variables will be evaluated by means of descriptive statistics. These tables will include observed values and changes from baseline values (the last observed ECG prior to the first study intervention administration will be used as baseline).

The ECG variables that will be analyzed are heart rate, PR interval, QRS interval, QT interval, and QT corrected for heart rate (QTc) interval using the following correction methods: QTc according to Bazett's formula (QTcB) and QTc according to Fridericia's formula (QTcF).

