Electrocardiogram data will be summarized by ECG parameter. The ECG variables that will be analyzed are heart rate, PR interval, QRS interval, QT interval, and QTc interval using the following correction methods: QTc according to Bazett's formula (QTcB) and QTcF (Bazett 1920, Fridericia 1920, Hodges 1983, ICH guidelines 2005).

Descriptive statistics of QTc intervals and changes from baseline will be summarized at each scheduled time point. The percentage of participants with QTc interval >450 milliseconds, >480 milliseconds, or >500 milliseconds will be summarized, as will the percentage of participants with QTc interval increases from baseline >30 milliseconds or >60 milliseconds. The last observed ECG prior to the first study intervention administration will be used as baseline.

All clinically relevant abnormalities in ECG waveform that are changes from the baseline readings will be reported (eg, changes in T-wave morphology or the occurrence of U-waves).

For the safety substudy, ECGs will be analyzed similarly to ECG statistical analysis as described above.

Vital Signs

Vital signs including pulse/heart rate and systolic and diastolic blood pressure (supine) will be summarized over time, using descriptive statistics and/or graphically. The percentage of participants with values beyond clinically important limits will be summarized.

Physical Examinations

Physical examination findings will be summarized at each scheduled time point.

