5.1.1. Analysis Phase Definition

The Prophylactic Dosing phase used for the safety evaluation and as defined below is extended compared to the Prophylactic Dosing phase as defined in the protocol considering the long half-life (~10 days) of the study intervention.

Following analysis phases are defined:

Table 1: Construction of analysis phases

Analysis phase Start date		End date		
Screening	The date &	& time of signing the 1 minute before date & time of first study drug intake**.		
(phase 1)	informed cor	nsent*		
Prophylactic	DosingDate & time	of first study drug intake**	Minimum of:	
(phase 2)	(JNJ - 64281	802 or Placebo)	a. Date of Day 50 Visit at 23.59h***	
			b. Date of study termination at 23.59h	
Follow-up	End of the P	rophylactic Dosing phase	Study termination date (date of last contact) at 23.59h	
(phase 3) ***	+1 minute			

^{*:} if no time is available then impute with 00:00

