5.1.2. Visit Windows

As participants do not always adhere to the protocol visit schedule, the following rules are applied to assign actual visits to analysis visits. Listed below are the visit windows and the target days for each visit. The reference day is the date of first study intervention intake. The relative day (reldy) of each visit will be defined as:

- reldy = visit date reference date + 1 for visits on or after Day 1,
- reldy= visit date reference date for visits before Day 1.

Consequently, there is no 'Day 0' defined.

If a participant has 2 or more actual visits in 1 visit window, the visit closest to the target day will be used as the protocol visit for that visit window. The other additional visit(s) will not be used in the summaries or analyses, but they can be used for determination of clinically important endpoints. If 2 actual visits are equidistant from the target day within a visit window, the later visit is used.

^{**} If no time is available and randomization happened on the same day, then impute with randomization time.

^{***} If no Day 50 Visit was performed, the date of first study intervention intake + 49 days will be used. Participants recruited under protocol version 1 (dd. 09NOV2021) or earlier will not have a Follow-up phase and will have their prophylactic phase ending at Study termination date (date of last contact) at 23:59h.

All assignments will be made in chronological order. Once a visit date is assigned to a visit window, it will no longer be used for a later time point. Listed below (Table 2]) are the analysis visit windows and the target days for each visit defined in the protocol.

Table 2: Visit Windows

Parameter	Analysis Phase	Scheduled Visit Number	Time Interval (label on output)	Time Interval (Day)*	Target Time Point (Day)
[Antiviral	[Screening]	[2]	[Baseline]	[<= 1]	[1]
Activity/	[Prophylactic]	[6]	[Day 5]	[1 to 7]	[5]
Immune]	[Prophylactic]	[10]	[Day 9]	[8 to 11]	[9]
	[Prophylactic]	[14]	[Day 13]	[12 to 15]	[13]
	[Prophylactic]	[18]	[Day 17]	[16 to 19]	[17]
	[Prophylactic]	[22]	[Day 21]	[20 to 23]	[21]
	[Prophylactic]	[26]	[Day 25]	[24 to 26]	[25]
	[Prophylactic]	[29]	[Day 28]	[27 to 34]	[28]
	[Prophylactic]	[30]	[Day 40]	[35 to 45]	[40]
	[Prophylactic]	[31]	[Day 50]	> 45	[50]
	[Follow-up]	[35]	[Day 90]	>45	[90]
[Clinical	[Screening]	[2]	[Baseline]	[<= 1]	[1]
Laboratory]	[Prophylactic]	-	[Unscheduled]	[1 to 11]	-
	[Prophylactic]	[14]	[Day 13]	[12 to 15]	[13]
	[Prophylactic]	-	[Unscheduled]	[16 to 26]	-

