5.6.3.3. Electrocardiogram

The ECG parameters as measured by the central monitoring that will be analyzed are heart rate, PR interval, RR interval, QRS interval, QT interval, and corrected QT (QTc) interval using the following correction methods: Bazett's formula (QTcB) and Fridericia's formula (QTcF)^{3,4}.

QTcB and QTcF values will be used as reported by central ECG lab, they will not be recalculated.

If ECG measurements are repeated at a visit, only the first measurement will be considered in the 'Visit' ECG result. The repeat measurements can be used for the worst TE grade/abnormality as explained below.

Descriptive statistics (mean, standard deviation, median and ranges) of actual ECG parameters and change from baseline will be summarized by intervention group at each scheduled time point.

The actual values for HR, PR, QRS, QTcB and QTcF and the changes from baseline for QTcB and QTcF will be categorized into abnormalities using the boundaries defined in Table 7.

Table 7:	Criteria for Abnor	rmal QTc Values and Ch	anges from Baseline

Abnormality class and label	ECG parameter			
	HR (bpm)	PR (ms)	QRS (ms)	QTcB and QTcF
Abnormalities for actual value	s		·	
Low	< 45	< 110	-	-
High	≥ 120	≥ 220	≥ 120	-
]450, 480] ms M/F (*)				> 450 - ≤ 480
]450, 480] ms M/F (*)				> 470 - \le 480
]480, 500] ms				> 480 - ≤ 500
> 500 ms				> 500
Abnormalities for change from	baseline		·	
]30, 60] ms				> 30 - ≤ 60
> 60 ms				> 60

^(*) The boundaries for QTcB and QTcF abnormalities are different for males and females, but the same abnormality label will be used.

No abnormalities will be defined for uncorrected QT, but uncorrected actual QT values >500 ms will be flagged and only shown in listings. Actual QTc values ≤ 450 ms are considered as normal, as well as all changes ≤ 30 ms.

Postbaseline abnormalities will be compared with their corresponding baseline result:

- TE will be concluded if the postbaseline value is above the upper limit and the baseline value is below the upper limit (eg, Normal or Low). The same applies to the postbaseline value being below the lower limit with the baseline value being above the lower limit (eg, Normal or High).
- If the baseline value is missing, a postbaseline abnormality will always be considered as TE.
- When changes from baseline are concerned (QTcB/QTcF), abnormality classes are always TE, per definition.

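### The SAP accepts an ECG up to 60 minutes after the first dose as baseline, even when a pre-dose ECG exists; the protocol requires a pre-dose baseline and SAP 6.2 does not list the change

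*SAP*

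**What the plan says.** **Protocol.** Section 9.4.4.1 states: "The last observed ECG prior to the first study intervention administration will be used as baseline". The Synopsis gives the same definition. Neither place allows a post-dose reading.

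**SAP, visit windows (5.1.2, Table 2).** The ECG baseline row covers relative day 1 or earlier, has target Day 1, is labelled Screening and carries the mark **. The note to that mark reads: "Up to 60 minutes after first study intervention intake". The note may appear apart from the table, among the text of Section 5.3.1. The attribution is secure, because no other row of Table 2 carries **, and the ** note to Table 1 deals with a different matter (imputing a missing intake time).

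**SAP, selection rule (5.1.2).** With two or more visits in a window, "the visit closest to the target day will be used as the protocol visit for that visit window". Then: "If 2 actual visits are equidistant from the target day within a visit window, the later visit is used". The same section also says that a visit date, once assigned to a window, is not used again for a later time point.

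**SAP, repeats (5.6.3.3).** "If ECG measurements are repeated at a visit, only the first measurement will be considered in the 'Visit' ECG result".

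**SAP, phases (5.1.1, Table 1).** Screening ends "1 minute before date & time of first study drug intake", and Prophylactic Dosing starts at that intake.

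**SAP 6.2** sets out the changes to the protocol-planned analyses. The ECG baseline is not among them.

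**The concern.** The baseline ECG feeds every ECG result in SAP 5.6.3.3: change from baseline, the QTc increase classes (above 30 and above 60 ms), treatment-emergent status, and the cross-tabulation of worst abnormality against baseline. A baseline recorded after dosing is not the one the protocol promises. In the active arms only, it could contain the start of any drug effect, which would shrink the measured change.

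A fallback for participants with no pre-dose ECG would be reasonable. The SAP does not write a fallback. It widens the baseline window for everyone and leaves the choice to a general rule that works on calendar days and favours the later visit. It also leaves the programmer with two tables that assign the same recording to different phases. A reader comparing the protocol with SAP 6.2 would not learn that the definition had moved.

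**Working it through.** There is no stated figure to reproduce. The check applies both definitions to example ECG times.

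**Inputs**
- Baseline window: relative day ≤ 1, target Day 1 (SAP Table 2).
- Relative day: visit date − date of first intake + 1 on or after Day 1, and visit date − date of first intake before it. There is no Day 0 (SAP 5.1.2). The scale is whole days, so ECGs before and after the dose on the same date are both Day 1.
- Post-dose limit: 60 minutes (note ** to Table 2).
- Choice: smallest distance |relative day − 1|, and on a tie the later visit (SAP 5.1.2).
- Protocol choice: last ECG before first intake (9.4.4.1).
- Dosing should start within 12 hours of the contact's consent (Protocol 1.3.2.1), so the screening ECG can fall on Day 1 or on Day −1.

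**Cases.** The clock times are illustrative, with the first dose at 10:00. Cases A, B and D assume separate visits.

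| Case | ECGs | Relative days | Distance to Day 1 | SAP baseline | Protocol baseline |
|---|---|---|---|---|---|
| A | 08:00 and 10:45, same day | 1, 1 | 0, 0 (tie) | 10:45, post-dose | 08:00 |
| B | 22:30 the evening before, and 10:45 | −1, 1 | 2, 0 | 10:45, post-dose | 22:30 |
| C | 10:45 only | 1 | 0 | 10:45, post-dose | none |
| D | 08:00 and 11:15 (75 min after dose) | 1, 1 | second ECG outside the limit | 08:00 | 08:00 |
| E | as A, but repeats at one visit | 1, 1 | first reading kept (5.6.3.3) | 08:00 | 08:00 |

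In A and B the SAP drops a valid pre-dose ECG. In C the SAP supplies a baseline where the protocol has none. In D and E the two agree.

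**Phase.** A 10:45 ECG lies after the 10:00 intake, so Table 1 puts it in Prophylactic Dosing, while Table 2 labels it Screening when it serves as baseline. The next ECG window in Table 2 also begins on Day 1, but the no-reuse sentence in 5.1.2 keeps the ECG out of that window. What remains open is the worst abnormality by phase (5.6.3.3), which follows phases and not visit windows. A reading compared with itself has change 0 and cannot be a new abnormality. The phase conflict could therefore affect who counts as having a Prophylactic-phase ECG, but could not create a treatment-emergent finding.

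**The case against.** **The SAP's rule seldom matters.** In the main study the only ECG scheduled before Day 28 is the one at screening; the PK substudy adds one at 48 hours. Displacing a pre-dose ECG needs a second, unscheduled ECG, at a separate visit, within 60 minutes after intake. The likelier purpose of the note is to rescue a single screening ECG recorded late (case C), which is a sensible use. This stands, and it limits the size of the problem. It does not change the rule as written, which has no such restriction.

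**The Table 2 note is a specific exception to Table 1.** That is a fair reading of intent. The SAP does not say so, and one sentence would settle it.

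**Stronger readings that the documents do not support**
- A reader might infer that the same ECG is counted as both baseline and a post-baseline visit. The no-reuse sentence in SAP 5.1.2 already bars this for by-visit results.
- A reader might infer that a known QTc effect is being hidden. Protocol 2.2 reports Phase 1 data supporting no effect on cardiac repolarization over the concentrations studied.
- A reader might put a figure on the dilution: with median time to peak of 7 to 10 hours, a straight-line rise gives 1/10 to 1/7, or about 10–14%, of the first-dose peak at 60 minutes. The straight line is an assumption, and the 7 to 10 hours sit in a section on an oral solution. No ECG is scheduled at the first-dose peak in any case, so this is not a measure of bias in the planned comparisons.
- A reader might add a meal effect. The documents give no basis for one, and all arms, including placebo, dose in fed conditions.

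**Conclusion.** The point holds as a definitional conflict of minor weight. The SAP permits a post-dose ECG baseline, the protocol does not, the change is not listed in SAP 6.2, and Tables 1 and 2 disagree on the phase of such an ECG. Because the allowance is not limited to participants without a pre-dose ECG, the selection rule would prefer a post-dose ECG from a separate visit (cases A and B). Repeats within one visit are unaffected.

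The numerical effect on QTc change from baseline is probably very small. That judgement rests on slow absorption in the Phase 1 data carrying over to this trial's formulation, and on extra ECGs in the first hour being rare. The documents give no count of affected participants, so neither can be confirmed from them. The analyses concerned are descriptive safety summaries, and no efficacy result depends on them.

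**What to change.** - In SAP 5.1.2 or 5.6.3.3, define the ECG baseline as the last pre-dose ECG. Use an ECG within 60 minutes after intake only when no pre-dose ECG exists. On the cases above this gives 08:00 for A, D and E, 22:30 for B, and 10:45 with a flag for C.
- State that a post-dose ECG used in this way is treated as Screening phase and is not counted in the worst treatment-emergent abnormality.
- Flag the participants whose baseline is post-dose and report their number by intervention group.
- List the departure from the protocol, with its reason, in SAP 6.2.

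The cost is a few sentences and one change to the baseline derivation. No extra data are needed, and no participant who has a baseline under the present SAP rule would lose it.

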5.3.2. Level of Significance

The superiority of JNJ-64281802 above placebo will be tested at 20% one-sided significance level to assess PoC.

5.3.3. Estimand

The primary estimand attributes are as follows.

Population

Healthy HHCs, aged 16 or 18 (depending on the legal age of consent in the jurisdiction in which the study is taking place) to 65 years inclusive, with a baseline 'target not detected (TND)' results for the DENV RT-qPCR assay and, if available, a negative/borderline NS1 protein assay result and with at least 1 post-baseline DENV RT-qPCR qualitative result up to and including the last day of dosing + 1 day.

Endpoint

Binary endpoint: presence or absence of a laboratory-confirmed DENV infection between baseline and last day of dosing + 1 day.

Interventions

Participants will receive a high- or low-dose JNJ-64281802 regimen, or matching placebo in a double-dummy fashion under fed conditions.

Intercurrent Events

- Prohibited medication (when considered as major protocol deviation).
- Missed doses and dose interruptions: Missing a loading dose (LD), 2 consecutive maintenance doses (MDs), or 2 nonconsecutive MDs within a week.
- Overdose of study intervention (when considered as major protocol deviation).
- Wrong study intervention (when considered as major protocol deviation).

These intercurrent events will be handled using a "treatment policy strategy" (ie, data will be used as observed), with participants included in the study intervention group as randomized.

Population-level Summary

Calculated prophylactic efficacy (=1 - odds-ratio ≈ 1 - relative risk).

5.3.4. Analysis Methods

Primary Estimator

The primary hypothesis of this study is that JNJ-64281802 is superior to placebo with respect to prevention of laboratory-confirmed DENV infection between baseline and last day of dosing.

The primary hypothesis will be evaluated based on the comparison between intervention groups using CIs, estimates, and p-values obtained from an exact logistic regression model adjusted for stratification factor region. The odds-ratio from the logistic regression model will be used to estimate the PE. Given the expected low incidence, this is expected to be similar to the PE estimated using the relative risk. The calculated prophylactic efficacy (= 1 - odds ratio ≈ 1 - relative risk rate) will be used as the population-level summary. The superiority of JNJ-64281802 above placebo will be tested at 20% one-sided significance level as a PoC. The individual 1-sided CIs for the prophylactic efficacy will be calculated from the regression model described above. This is the primary efficacy analysis. As a secondary estimator, the Mantel-Haenszel stratum-weighted estimator of the risk difference, adjusted for the stratification factor region will be calculated together with the associated CIs.

The primary objective will be assessed using the following hierarchical hypothesis testing approach:

- 1. In the first step, the HDR will be compared with placebo.
- 2. If a significant reduction in laboratory-confirmed DENV infections is established for the HDR, the LDR will be compared with placebo with regards to the primary endpoint.

Subgroup Analyses

Subgroup analyses will be performed by geographic region (American Continent, Southeast Asia), country, serostatus at baseline (seronegative, defined as IgG < 22 RU/mL, seropositive defined as $IgG \ge 22 \text{ RU/mL}$) and age (<40 years, >=40 years) upon the condition that at least 6 cases are observed in the subgroup and over the combined placebo and active study intervention group for which the comparison is done.

5.4. Secondary Endpoint(s) Analysis

5.4.1. Key Secondary Endpoint(s)

5.4.1.1. Definition of Endpoint(s)

The key secondary endpoint is defined as presence or absence of laboratory-confirmed symptomatic DENV infection between baseline and last day of dosing + 1 day. Laboratory-confirmed symptomatic DENV infection is defined as having at least 2 solicited systemic AEs, of which at least one is a most common dengue symptom (see Table 3), lasting for ≥ 1 day and

occurring within a +/-2 days time window around the positive PCR or NS1 test. If a sample is missing and the next or prior available sample is positive for a DENV infection, the missing sample will be considered as positive for DENV infection as well. Consequently, solicited AEs observed within +/-2 days around the scheduled missing sample date will be considered as well as a confirmation of a symptomatic DENV infection.

Table 3: Solicited systemic AEs

- Retro-orbital pain*	- Fever*	- Fatigue	- Vomiting
- Abdominal pain	- Headache *	- Myalgia *	- Diarrhea
- Arthralgia*	- Nausea	- Loss of appetite	- Rash *

^{*} Most common dengue symptom

